### For Participants with Non-Measurable Disease (i.e., Non-Target Disease)

Non-Target Lesions	New Lesions	Overall Response
CR	No	CR
Non-CR/non-PD	No	Non-CR/non-PD*
Not all evaluated	No	not evaluated
Unequivocal PD	Yes or No	PD
Any	Yes	PD

* ‘Non-CR/non-PD’ is preferred over ‘stable disease’ for non-target disease since SD is increasingly used as an endpoint for assessment of efficacy in some trials so to assign this category when no lesions can be measured is not advised
		

#### 11.1.5 Duration of Response

Duration of overall response: The duration of overall response is measured from the time measurement criteria are met for CR or PR (whichever is first recorded) until the first date that recurrent or progressive disease is objectively documented (taking as reference for progressive disease the smallest measurements recorded since the treatment started, or death due to any cause. Participants without events reported are censored at the last disease evaluation).

Duration of overall complete response: The duration of overall CR is measured from the time measurement criteria are first met for CR until the first date that progressive disease is objectively documented, or death due to any cause. Participants without events reported are censored at the last disease evaluation.

Duration of stable disease: Stable disease is measured from the start of the treatment until the criteria for progression are met, taking as reference the smallest measurements recorded since the treatment started, including the baseline measurements.

CONFIDENTIAL

*This document is confidential. Do not disclose or use except as authorized.*

IRB APPROVED

#### **11.1.6 Progression-Free Survival**

**Overall Survival:** Overall Survival (OS) is defined as the time from randomization (or registration) to death due to any cause, or censored at date last known alive.

**Progression-Free Survival:** Progression-Free Survival (PFS) is defined as the time from randomization (or registration) to the earlier of progression or death due to any cause. Participants alive without disease progression are censored at date of last disease evaluation.

**Time to Progression:** Time to Progression (TTP) is defined as the time from randomization (or registration) to progression, or censored at date of last disease evaluation for those without progression reported.

#### **11.1.7 Response Review**

For trials where the response rate is the primary endpoint, it is strongly recommended that all responses be reviewed by an expert(s) independent of the study at the study's completion. Simultaneous review of the participants' files and radiological images is the best approach.

### **12. DATA REPORTING / REGULATORY REQUIREMENTS**

Instructions for AE reporting can be found in Section 7.

#### **12.1 Data Reporting**

##### **12.1.1 Method**

The ODQ will collect, manage, and perform quality checks on the data for this study.

##### **12.1.2 Responsibility for Data Submission**

Study team is responsible for submitting data and/or data forms to the ODQ according to the schedule set by the ODQ.

#### **12.2 Data Safety Monitoring**

The DF/HCC Data and Safety Monitoring Committee (DSMC) will review and monitor toxicity and accrual data from this study. The committee is composed of clinical specialists with experience in oncology and who have no direct relationship with the study. Information that raises any questions about participant safety will be addressed with the Overall PI and study team.

---

*CONFIDENTIAL*

*This document is confidential. Do not disclose or use except as authorized.*

**IRB APPROVED**

The DSMC will review each protocol up to four times a year or more often if required to review toxicity and accrual data. Information to be provided to the committee may include: up-to-date participant accrual; current dose level information; DLT information; all grade 2 or higher unexpected adverse events that have been reported; summary of all deaths occurring with 30 days of intervention for Phase I or II protocols; for gene therapy protocols, summary of all deaths while being treated and during active follow-up; any response information; audit results, and a summary provided by the study team. Other information (e.g. scans, laboratory values) will be provided upon request.

### **12.3 Multi-Center Guidelines**

This protocol will adhere to the policies and requirements of the DF/HCC Multi-Center Data and Safety Monitoring Plan. The specific responsibilities of the Overall PI, Coordinating Center, and Participating Institutions and the procedures for auditing are presented in Appendix E.

- The Overall PI/Coordinating Center is responsible for distributing all IND Action Letters or Safety Reports to all participating institutions for submission to their individual IRBs for action as required.
- Mechanisms will be in place to ensure quality assurance, protocol compliance, and adverse event reporting at each site.
- Except in very unusual circumstances, each participating institution will order the study agent(s) directly from supplier. A participating site may order the agent(s) only after the initial IRB approval for the site has been forwarded to the Coordinating Center.

### **13. STATISTICAL CONSIDERATIONS**

Prior to Amendment 7, patients with DTC, MTC, and ATC were randomized to Arms 1 and 2. With approval of Amendment 7, patients with ATC were no longer randomized into Arms 1 and 2, but rather registered into Arm 3 (for a total of n=7 patients with ATC entered into Arms 1, 2, and 3). With approval of Amendment 12, the accrual for the ATC cohort was increased to n=10.

The primary objective of this trial is to evaluate efficacy in terms of best overall response rate (CR+PR) for patients with DTC. The purpose of the randomization with nivolumab and ipilimumab starting sequentially is to provide opportunities via the correlatives to study the specific immunologic changes that occur in response to either drug alone as well as both drugs in combination. Although patients will be randomized between arms, no differences in terms of efficacy are expected, therefore, for the primary endpoint of response, the arms will be analyzed together.

A two -stage design (Simon's minimax design) will be used to minimize the number of pts enrolled. Twenty-three eligible patients with differentiated thyroid cancer (DTC) who start protocol treatment are to be accrued in the first stage. If there are  $\leq$  2 patients with DTC with

---

*CONFIDENTIAL*

*This document is confidential. Do not disclose or use except as authorized.*

**IRB APPROVED**

disease in response, accrual to this trial will be closed with the expectation that there is little evidence that the response rate will reach 25%. The probability that the trial will close early is 59% if the true response rate is 10%. If there are >2 patients with DTC with disease in response, accrual will continue until a total of 32 eligible patients with DTC who start protocol treatment are entered. If there are >5 patients with DTC with disease in response among 32 eligible patients with DTC who began protocol treatment, further testing of this regimen will be considered. If the true response rate is 25%, the probability of concluding the regimen is effective is 84%, if the true response rate is 10%, the probability of concluding the regimen is effective is 9%. In addition, n=7 medullary and n=10 anaplastic thyroid patients will also be included as exploratory cohorts. Allowing for patients to be declared ineligible and/or not start protocol treatment after registration, a total of 54 pts will be entered into Arms 1, 2, and 3. The following stratification factor will be used for Arms 1 and 2 only in order to prevent imbalance across treatment arms:

- Histology (differentiated thyroid cancer vs. medullary thyroid cancer)

(Prior to Amendment 7, patients with anaplastic thyroid cancer were also randomized, and as of approval of Amendment 7, patients with anaplastic thyroid cancer will no longer be randomized, they will instead be entered into Arm 3 (see schema and section 5 for details)).

The primary efficacy population includes all eligible patients with DTC who begin protocol treatment. Best overall response will be summarized as a proportion with a corresponding exact 95% confidence interval (CI) (if the trial closes to accrual after the first stage), or a corresponding 95% two-stage CI if the trial closes to accrual after the second stage. Best overall response for patients with medullary and anaplastic thyroid cancer will also be summarized.

For secondary objectives: Adverse events will be classified and graded according to the CTCAE v.4.0. Frequencies of adverse events will be summarized among patients who begin protocol therapy overall and within histologic type. The distributions of progression and survival will be estimated within histologic subtype using a Kaplan-Meier method with corresponding 95% confidence intervals for the median or time-specific event time. Several correlative studies are also planned. Given the small sample size of this trial, these studies are exploratory. Samples will be collected at baseline and at post-baseline timepoints as outlined in the protocol. Markers from the patients with evaluable samples will be summarized descriptively and graphically. Within subject changes in markers will also be analyzed. Assuming 32 patients with DTC with baseline and a post-baseline value provides 82% power to detect .54 SD mean difference (Wilcoxon sign rank test two-sided 0.05 alpha level). Markers from the patients with evaluable samples within medullary and anaplastic thyroid cancer will also be summarized descriptively.

With an estimated monthly accrual of 1-2 patients, the first stage of accrual for patients with DTC is estimated to complete accrual in approximately 18 months. Due to possible delays in initiation of approval at other sites, in initiation of accrual itself, accrual to the first stage could take 24 months. As is customary with this type of design, accrual will be suspended after the first stage (n=23 eligible patients) in order to assess outcome; however, this suspension is also dependent on the actual observed accrual rate and the number of patients with confirmation of disease response status while the first stage of the trial is accruing

## 14. PUBLICATION PLAN

The results should be made public within 24 months of reaching the end of the study. The end of the study is the time point at which the last data items are to be reported, or after the outcome data are sufficiently mature for analysis, as defined in the section on Sample Size, Accrual Rate and Study Duration. If a report is planned to be published in a peer-reviewed journal, then that initial release may be an abstract that meets the requirements of the International Committee of Medical Journal Editors. A full report of the outcomes should be made public no later than three (3) years after the end of the study.

**APPENDIX A                    PERFORMANCE STATUS CRITERIA**

ECOG Performance Status Scale		Karnofsky Performance Scale	
Grade	Descriptions	Percent	Description
0	Normal activity. Fully active, able to carry on all pre-disease performance without restriction.	100	Normal, no complaints, no evidence of disease.
		90	Able to carry on normal activity; minor signs or symptoms of disease.
1	Symptoms, but ambulatory. Restricted in physically strenuous activity, but ambulatory and able to carry out work of a light or sedentary nature (e.g., light housework, office work).	80	Normal activity with effort; some signs or symptoms of disease.
		70	Cares for self, unable to carry on normal activity or to do active work.
2	In bed <50% of the time. Ambulatory and capable of all self-care, but unable to carry out any work activities. Up and about more than 50% of waking hours.	60	Requires occasional assistance, but is able to care for most of his/her needs.
		50	Requires considerable assistance and frequent medical care.
3	In bed >50% of the time. Capable of only limited self-care, confined to bed or chair more than 50% of waking hours.	40	Disabled, requires special care and assistance.
		30	Severely disabled, hospitalization indicated. Death not imminent.
4	100% bedridden. Completely disabled. Cannot carry on any self-care. Totally confined to bed or chair.	20	Very sick, hospitalization indicated. Death not imminent.
		10	Moribund, fatal processes progressing rapidly.
5	Dead.	0	Dead.

---

## **APPENDIX D METHODS OF CONTRACEPTION**

At a minimum, subjects must agree to use one highly effective OR one less effective method of contraception as listed below:

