### **3. PARTICIPANT SELECTION**

Participants must meet the following inclusion criteria on screening examination to be eligible to participate in the study:

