- Total Bilirubin  $\leq 1.5 \times \text{ULN}$  (except subjects with Gilbert Syndrome, who can have total bilirubin  $< 3.0 \text{ mg/dL}$ )

7. Ability to understand and the willingness to sign a written informed consent document.

8. Women of childbearing potential (WOCBP) must use appropriate method(s) of contraception. WOCBP should use an adequate method to avoid pregnancy for 23 weeks (30 days plus the time required for nivolumab to undergo five half-lives) after the last dose of investigational drug

9. Women of childbearing potential must have a negative serum or urine pregnancy test (minimum sensitivity 25 iu/l or equivalent units of hcg) at screening. Pregnancy test will be repeated on the day of the first dose of study drug (before administration), although results of this test are not required for registration.

*“Women of childbearing potential” is defined as any female who has experienced menarche and who has not undergone surgical sterilization (hysterectomy or bilateral oophorectomy) or who is not postmenopausal. Menopause is defined clinically as 12 months of amenorrhea in a woman over 45 in the absence of other biological or physiological causes.*

10. Men who are sexually active with WOCBP must use any contraceptive method with a failure rate of less than 1% per year. Men receiving nivolumab and who are sexually active with WOCBP will be instructed to adhere to contraception for a period of 31 weeks after the last dose of investigational product. Women who are not of childbearing

---

CONFIDENTIAL

*This document is confidential. Do not disclose or use except as indicated.*

IRB APPROVED

potential (ie, who are postmenopausal or surgically sterile as well as azoospermic men do not require contraception

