### **Highly Effective Methods of Contraception**

Highly effective methods of contraception have a failure rate of < 1% when used consistently and correctly. WOCBP and female partners of male subjects, who are WOCBP, are expected to use one of the highly effective methods of contraception listed below. Male subjects must inform their female partners who are WOCBP of the contraceptive requirements of the protocol and are expected to adhere to using contraception with their partner. Contraception methods are as follows:

1. Progestogen only hormonal contraception associated with inhibition of ovulation.
2. Hormonal methods of contraception including oral contraceptive pills containing combined estrogen + progesterone, vaginal ring, injectables, implants and intrauterine devices (IUDs) such as Mirena®
3. Nonhormonal IUDs, such as ParaGard®
4. Bilateral tubal occlusion
5. Vasectomised partner with documented azoospermia 90 days after procedure
  - Vasectomised partner is a highly effective birth control method provided that partner is the sole sexual partner of the WOCBP trial participant and that the vasectomised partner has received medical assessment of the surgical success.
6. Intrauterine hormone-releasing system (IUS).
7. Complete abstinence
  - Complete abstinence is defined as the complete avoidance of heterosexual intercourse.
  - Complete abstinence is an acceptable form of contraception for all study drugs and must be used throughout the duration of the study treatment (plus 5 half-lives of the investigational drug plus 30 days).
  - It is not necessary to use any other method of contraception when complete abstinence is elected.
  - Subjects who choose complete abstinence must continue to have pregnancy tests
  - Acceptable alternate methods of highly effective contraception must be discussed in the event that the subject chooses to forego complete abstinence.
  - The reliability of sexual abstinence needs to be evaluated in relation to the duration of the clinical trial and the preferred and usual lifestyle of the subject.

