### **Less Effective Methods of Contraception**

1. Diaphragm with spermicide
2. Cervical cap with spermicide
3. Vaginal sponge with spermicide
4. Male or female condom with or without spermicide\*
5. Progestogen-only oral hormonal contraception, where inhibition of ovulation is not the primary mode of action

\* A male and a female condom must not be used together.

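### Appendix D sets the contraception minimum at one less effective method, below its own highly effective standard and, by inference, below inclusion criterion 10 for men

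*Combined protocol and SAP*

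**What the plan says.** Appendix D (Methods of Contraception) begins with a floor for all participants: "At a minimum, subjects must agree to use one highly effective OR one less effective method of contraception as listed below". Three lists follow: highly effective, less effective and unacceptable methods.

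Under Highly Effective Methods, the class is defined as follows: "Highly effective methods of contraception have a failure rate of < 1% when used consistently and correctly". The same paragraph says who should use it: "WOCBP and female partners of male subjects, who are WOCBP, are expected to use one of the highly effective methods of contraception listed below". It adds that "Male subjects must inform their female partners who are WOCBP of the contraceptive requirements of the protocol". The list has 7 items. Under the abstinence item, a participant who gives up abstinence has to be offered a discussion of highly effective alternatives.

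The Less Effective Methods list has 5 items. Item 4 reads "Male or female condom with or without spermicide". No failure rate is given for any item in this list.

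Section 3.1 treats the sexes differently. Criterion 8 says that WOCBP "must use appropriate method(s) of contraception", with no failure-rate threshold, and continues for 23 weeks after the last dose. Criterion 10 says that men sexually active with WOCBP "must use any contraceptive method with a failure rate of less than 1% per year", and continues for 31 weeks after the last dose. Women not of childbearing potential and azoospermic men are exempt. Neither criterion refers to Appendix D.

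**The concern.** A minimum should not sit below the standard it supports. Here the binding sentence of the appendix accepts a single less effective method, while the next paragraph asks the same women for a highly effective one. If the first sentence governs, the second has no force. If the second governs, the alternative offered in the first is a mistake. For men, the floor also falls below a mandatory eligibility criterion.

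Appendix D is the only place in the documents that lists methods, and it is a natural reference for sites after enrolment, when the eligibility check is over but the obligation continues. The nivolumab background in Section 2.2 reports developmental toxicity in pregnant monkeys: more fetal and neonatal deaths without overt toxicity to the mothers. A low stated floor therefore weakens a control on a recognised risk. The protocol's other measures are pregnancy tests and reporting of pregnancies to the drug supplier within 24 hours (Section 7.11). These detect a pregnancy but do not prevent one.

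**Working it through.** No sample size, power or error rate is involved, so the check is a comparison of texts with some simple counts.

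**Texts side by side**

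| Place | Who | Standard | Force |
|---|---|---|---|
| Appendix D, opening sentence | All participants, as worded | Any one method, highly or less effective | Must |
| Appendix D, Highly Effective Methods | WOCBP, and WOCBP partners of male participants | Highly effective (failure under 1% with consistent, correct use) | Expected |
| Section 3.1, criterion 8 | WOCBP | Appropriate or adequate method, no threshold | Must (appropriate); should (adequate) |
| Section 3.1, criterion 10 | Men sexually active with WOCBP | Failure under 1% per year | Must |

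**Step 1: what meets the floor.** Appendix D lists 7 highly effective and 5 less effective methods: 7 + 5 = 12. The opening sentence accepts one from either list, so all 12 suffice alone, including a condom without spermicide.

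**Step 2: within the appendix.** The floor covers WOCBP, and the next paragraph expects those same women to use one of the 7. The floor is therefore 5 methods wider than the expectation. The instruction on giving up abstinence also points to highly effective methods only, although it requires discussion and not use.

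**Step 3: against criterion 10.** The highly effective class is defined by failure under 1%. Methods placed in a separate, less effective class are, by the protocol's own classification, outside that level. On this inference, a man relying on a condom alone meets the appendix floor but not criterion 10. The two thresholds are also worded differently: the appendix specifies consistent and correct use but no time unit, while criterion 10 says per year but gives no condition of use.

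**Step 4: against criterion 8.** There is no direct conflict, because criterion 8 sets no threshold. For the same reason, the Appendix D floor is the only explicit minimum that women have.

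**Step 5: reach and duration.** Section 13 plans 54 patients in all, which is the ceiling. Only WOCBP, or men sexually active with WOCBP, who rely on a less effective method alone are affected, and the documents give no basis for estimating that share. Treatment lasts at most 24 months (Section 5.6), or about 2 × 52 = 104 weeks. The longest contraception period is then:

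- women: 104 + 23 = 127 weeks, and 127 / 52 = about 2.4 years
- men: 104 + 31 = 135 weeks, and 135 / 52 = about 2.6 years

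These durations show how long the rule applies. They do not measure harm.

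**Step 6: detection.** The Study Calendar (Section 10) places pregnancy tests at screening, day 1 of each cycle and End of Treatment. It shows none in the 23 weeks that follow the last dose, although the calendar's layout is imperfect in the copy reviewed.

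**The case against.** The strongest defence is that the two tiers are deliberate: a minimum for everyone and a preferred standard for those at risk. The softer verb in the second paragraph and the separate lists fit that reading. On this view, requiring only highly effective methods for women is a policy preference, since criterion 8 does not demand it. Men are already covered, because Section 3 states that "Participants must meet the following inclusion criteria on screening examination" and Section 4.1 requires an investigator to confirm eligibility. A general appendix does not waive a specific, stricter criterion.

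Much of this stands. No man becomes eligible through Appendix D, there is no clash with criterion 8, and the documents do not say which sentence of the appendix prevails. The animal data concern directly dosed pregnant females and do not address conception by a treated man, so the harm argument applies mainly to women. The condom shortfall is an inference. The consent form and eligibility checklist are not in the documents, so what participants are actually told cannot be seen.

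The two-tier reading still does not reconcile the texts. The higher expectation is addressed to the very people for whom contraception matters, which leaves no at-risk group for whom the lower floor is the intended standard. For men, the floor lies below a binding rule. Either reading needs an edit.

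**Conclusion.** The concern holds as a minor inconsistency in a safety provision. The mandatory minimum in Appendix D is lower than the standard stated in the paragraph after it and, by inference, lower than criterion 10. The finding within the appendix rests on the text alone. The criterion 10 part also assumes that methods classed as less effective do not reach failure under 1% per year.

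In practice the reach is limited to an unknown share of at most 54 patients. For men, criterion 10 at eligibility and the duty to inform partners limit it further. Nothing in the two-stage design, the response endpoint, the analysis populations or the planned analyses changes.

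**What to change.** Make three wording changes in one amendment:

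1. In the opening sentence of Appendix D, remove the alternative of one less effective method, so that the minimum is one highly effective method.
2. Label the less effective list as not sufficient when used alone.
3. Have criteria 8 and 10 both refer to the Appendix D highly effective standard, with one threshold: failure under 1% per year when used consistently and correctly.

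The cost is drafting, plus a narrower choice. For women, the methods acceptable alone fall from 12 to 7. For men, nothing is added beyond what criterion 10 already requires. However, 5 of the 7 highly effective methods (items 1 to 4 and 6) are used by the female partner, so a man's compliance often depends on her. The consent form and eligibility checklist should be checked against the new wording.
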